3. Current active hepatic or biliary disease (with exception of liver disease secondary to chronic GVHD, or patients with Gilbert's syndrome, asymptomatic gallstones, or stable chronic liver disease per investigator assessment)
 - **Patients with abnormal liver function tests (bilirubin, alkaline phosphatase, ALT, AST) due to chronic GVHD are specifically not excluded from the study. This is a common manifestation of chronic GVHD, and thus a major target for the study therapy.**
4. Treatment with experimental non-FDA approved therapy within 5 terminal half lives or 4 weeks prior to enrollment, whichever is longer
5. Other past or current solid tumor malignancy
 - **Subjects who have been free of malignancy for at least 5 years, or have a history of completely resected non-melanoma skin cancer, or successfully treated in situ carcinoma are eligible.**

6. Prior treatment with anti-CD20 monoclonal antibody or alemtuzumab within 3 months prior to start of therapy.
7. **Uncontrolled** infectious complications not responsive to appropriate antimicrobial therapy.
8. History of significant cerebrovascular disease (i.e. stroke or TIA) in the past 6 months or ongoing event with active symptoms or sequelae
9. HIV positivity
10. Uncontrolled, current significant cardiac disease including unstable angina, acute myocardial infarction within six months prior to randomization, congestive heart failure (NYHA III-IV), and arrhythmia unless controlled by therapy, with the exception of extra systoles or minor conduction abnormalities.
 - **Patients with history of cardiac disease, such as coronary disease, arrhythmia or congestive heart failure that are on appropriate medical therapy and without evidence of current decompensation are eligible.**
11. Significant concurrent, **uncontrolled** medical condition including, but not limited to, renal, hepatic, gastrointestinal, endocrine, pulmonary, neurological, cerebral or psychiatric disease which in the opinion of the investigator may represent a risk for the patient.
 - **Those patients with medical conditions that are controlled with medical therapy are eligible.**
12. Clinically active Hepatitis B defined as positive HBsAg; or positive HBcAb with detectable HBV DNA viral load. Patients who are HBcAb with undetectable HBV DNA viremia are eligible.
13. Positive serology for hepatitis C (HC) defined as a positive test for HCAb and confirmed by HC RIBA or HCV RNA viral load
14. Screening laboratory value exclusion criteria:

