 - platelets
(no minimum platelet count is required by this trial, as this is a frequent manifestation of poor-risk chronic GVHD, and such patients may benefit from this protocol therapy)
 - neutrophils $<1.0 \times 10^9/L$
(neutrophil count should be >1000 without growth factor support, unless neutropenia is caused by anti-neutrophil antibodies or other manifestation of chronic GVHD)
 - creatinine >2.0 times upper normal limit
 - total bilirubin >1.5 times upper normal limit (**unless due to chronic GVHD**)
 - ALT >2.0 times upper normal limit (**unless due to chronic GVHD**)

- alkaline phosphatase >2.5 times upper normal limit (**unless due to chronic GVHD**)

15. Pregnant or lactating women. Women of childbearing potential must have a negative pregnancy test at screening.
16. Women of child bearing potential must undergo pregnancy testing within 7 days of the first dose of study therapy. Women must also undergo pregnancy test at 6 months after the last dose.
17. Women of childbearing potential, including women whose last menstrual period was less than one year prior to screening, unable or unwilling to use adequate contraception from study start to one year after the last dose of protocol therapy. Adequate contraception is defined as hormonal birth control, intrauterine device, double barrier method or total abstinence.
18. Male subjects unable or unwilling to use adequate contraception methods from study start to one year after the last dose of protocol therapy.

IV. STUDY THERAPY

i. Prednisone therapy

Starting dose of prednisone will be 1mg/kg body weight per day. If patients are treated with alternative steroid agents (e.g. methylprednisolone), this should be dosed to the corresponding prednisone equivalent of 1 mg/kg actual body weight.

The specific duration of prednisone therapy and tapering schedule for prednisone is not dictated by this protocol. However, the following serves as a guide for management of prednisone and other immune suppressive agents:

1. Start prednisone at 1 mg/kg/day
2. Continue this dose for 2-4 weeks or longer as needed in the setting of ongoing clinical improvement in chronic GVHD manifestations
3. With stable or improving chronic GVHD manifestations, begin taper on an every 1-2 week schedule with a target of reaching 0.5mg/kg/day
4. Continue 0.5mg/kg/day for 4 week plateau
5. Then taper by 10-20% of total dose per month as tolerated

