The use of topical agents for control of chronic GVHD manifestations is part of usual clinical care for affected patients. Common examples include various eye drops and artificial tears for ocular sicca, steroid or other immune suppressive agent mouth rinses for oral involvement, or topical steroid creams for mild cutaneous involvement. Use of these agents for patients on study will not be controlled or directed by this protocol. Rather, use of these agents will be directed by treating clinicians as part of usual clinical care. Use of these agents will be recorded in data capture on each study visit. Use of these non-systemic therapies will not inform study endpoints that include requirement for additional systemic immune suppressive therapies.

iv. Supportive antimicrobial prophylaxis on study

- i. All patients on study must receive antimicrobial prophylaxis per BMT guidelines and standards for the prevention of bacterial, viral, fungal, and pneumocystis infections.

V. STUDY OUTCOMES/ANALYSIS ENDPOINTS

1. Safety

a. Definition of DLT for phase I component:

- i. In the phase I study, dose escalation will proceed as previously described. The dose limiting toxicity (DLT) will be defined using CTCAE version 4.0 as the following:
 - Events occurring within 46 days of the last dose of drug (4 half-lives) that are:
 - a) Grade 4 infusion reactions,
 - b) Grade 4 constitutional symptoms at least possibly due to ofatumumab,
 - c) Grade 3 organ toxicities (neurologic, pulmonary, cardiac, gastrointestinal, genitourinary, hepatic, cutaneous) at least possibly due to ofatumumab,
 - d) Grade 4 neutropenia lasting more than 14 days
- ii. Importantly, known infusional toxicities of ofatumumab are managed appropriately with modification of infusion rate or temporary halting of infusion, as well as with supportive care including IV fluids, anti-histamines, and steroids.
- iii. Specifically, grade 1-3 infusion-associated adverse events defined by CTC version 4.0 are not considered DLT in this trial. The occurrence of grade 4 infusion-associated adverse event is considered DLT.
- iv. According to observed toxicities in the phase I component, the greatest dose tolerated in the dose escalation will be carried forward into the phase II component of the trial as the recommended phase II dose.
- v. Events clearly related to chronic GVHD, relapse of the primary hematological disorder, concurrent medication, or infection will not be included as a DLT.

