From whole blood samples, plasma will be separated, and utilized for determination of soluble BAFF levels by enzyme-linked immunosorbent assay (ELISA). From peripheral blood mononuclear cells (PBMC), B cells will be isolated. Antibodies targeting surface antigens CD19, CD20, CD38, CD27, and IgD will be utilized for staining, and the respective cell subsets will be characterized by flow cytometry according to phenotype: Naïve B cells (IgD⁺CD38^{Low}CD27⁻), transitional B cells (IgD⁺CD38^{High}CD27⁻), IgD⁺ memory B cells (IgD⁺CD38^{Low}CD27⁺), pre-germinal center B cells (IgD⁺CD38^{High}CD27⁺), post-germinal center memory B cells (IgD^{Low}CD38^{Low}CD27⁺), and plasmablast/plasma cell (IgD^{Low}CD38^{High}CD27⁺).

3. Summary of pre-treatment and on-study testing to be performed

- Pre-treatment assessments / screening

- i. Evaluation of eligibility: Inclusion, exclusion criteria
- ii. Laboratory studies (CBC with differential, chemistry, liver function tests, review of prior hepatitis B and C, as well as HIV testing – may utilize prior HIV/hepatitis testing done for purpose of transplant eligibility)
- iii. Pregnancy - Women of childbearing potential must have current negative pregnancy test, and both men and women must agree to adequate contraception methods.
- iv. EKG
- v. assessment of Karnofsky Performance Status (KPS)

- On-study assessments (windows described in study calendar)

- i. history and physical examination, standard laboratory tests (CBC, chemistry, LFT)
- completed screening, day 0, day 14, months 1, 3, 6, 9, 12, 18, 24
- ii. Chronic GVHD activity
- completed screening, day 14, months 1, 3, 6, 9, 12, 18, 24
- includes scoring of chronic GVHD severity per NIH 0-3 severity, clinician-reported severity measures, patient reported severity
- includes recording of immune suppressive medications at each visit
- iii. Patient-reported outcomes
- completed screening, day 14, months 1, 3, 6, 9, 12, 18, 24

- includes quality of life, Lee symptom scale, and HAP (human activity profile)

iv. Functional measures

- completed screening, day 14, months 1, 3, 6, 9, 12, 18, 24

- includes grip strength and 2 minute walk test

v. Biologic samples

- baseline, then months 3, 6, 12

- includes the above-described B cell subset studies and BAFF levels

4. Criteria for patient termination from study

a. Patient decision to withdraw from study

b. Death

c. Relapse of primary hematologic malignancy

d. End of study

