If at any time the subject meets any of the liver chemistry stopping criteria, then proceed as described above

If after 4 weeks of monitoring, ALT<3xULN and bilirubin<2xULN monitor twice monthly until liver chemistries normalize or return to within baseline values

- b. **Pregnancies:** Pregnancies must be reported to Novartis; however are not to be reported as SAEs unless they meet serious criteria.

2. Special safety monitoring requirements on study:

a. **Hepatitis B Screening**

Follow-up monitoring must be included in the study protocol:

- If HBV DNA is negative, subject may be included
- Monitoring during the follow-up period will be performed during routine study visits for a minimum follow-up period of six months after the last dose, as long as the subject remains on study. Monitoring frequency during follow-up should occur at a minimum of every 3 months. Whenever possible, the monitoring should occur as part of the routine follow-up visit
- Prophylactic antiviral therapy, in addition to the monitoring described above, may be initiated at the discretion of the investigator.

HBsAg positive (regardless of other Hepatitis B serologies):

- exclude

HBsAg negative, HBcAb negative, HBsAb positive

- include

HBsAg negative, HBcAb positive (regardless of HBsAb status)

HBV DNA must be performed

- if HBV DNA is positive the subject is excluded

- If HBV DNA is negative, subject may be included but must undergo at least every 2 month HBV DNA PCR testing from the start of treatment during the treatment course.
- Monitoring during the on treatment periods is required at least every 2 months and during follow-up at a minimum of every 2-3 months up to 6 months after the last dose.
- Prophylactic antiviral therapy, in addition to the monitoring described above, may be initiated at the discretion of the investigator.

If the subjects' HBV DNA becomes positive during the study, the investigator should manage the clinical situation as per the standard of care of that institution, and the Novartis medical monitor should be notified. The risks and benefits of continuing ofatumumab or discontinuing ofatumumab should be discussed with the medical monitor before appropriate treatment decisions are made for that individual subject.

b. Progressive Multifocal Leukoencephalopathy (PML)

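### Hepatitis B eligibility may be judged on pre-transplant results of any age, so a patient who has become positive since transplant can be dosed without a current test

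*Combined protocol and SAP*

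**What the plan says.** Section III, exclusion 12, keeps out "Clinically active Hepatitis B defined as positive HBsAg; or positive HBcAb with detectable HBV DNA viral load". Patients who are HBcAb positive with undetectable HBV DNA may enter. No test date or window is attached.

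Section V.3 describes how status is established. The pre-treatment list asks for a blood count, chemistry and liver tests, and for a review of earlier hepatitis B, hepatitis C and HIV testing. It adds that sites "may utilize prior HIV/hepatitis testing done for purpose of transplant eligibility". No maximum age is given.

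The Hepatitis B Screening text in section VII then sorts patients by serology:

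- HBsAg positive: excluded.
- "HBsAg negative, HBcAb negative, HBsAb positive": included, with no further test asked for.
- HBsAg negative and HBcAb positive: "HBV DNA must be performed". A positive DNA result excludes. A negative one allows entry with repeat DNA testing at least every 2 months during treatment.

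On antivirals it says: "Prophylactic antiviral therapy, in addition to the monitoring described above, may be initiated at the discretion of the investigator". The Study Calendar has screening entries for CBC and liver tests, ECG and pregnancy test, but no hepatitis B row.

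**The concern.** The exclusion describes the patient's condition now, but the permitted evidence may describe it before the transplant. Everyone in this trial has since had conditioning, a transplant and immune suppression, and has developed chronic GVHD. A result obtained for transplant eligibility predates all of that.

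At stake is the safety of the individual patient. Ofatumumab is given on days 0 and 14 on top of 1 mg/kg/day prednisone. The protocol's own summary of the rheumatoid arthritis study reports B-cell levels below the normal range or baseline for roughly 20 to 34 months after these doses. Withholding the second infusion cannot undo the first, so the check is useful only if it comes before day 0.

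**Working it through.** No arithmetic applies. The check is to follow a patient through every hepatitis B provision and see where a current test is required.

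**Step 1: which results count.** Section V.3 accepts transplant-eligibility results without an age limit. The protocol does set currency where it wants it: the next item in the same list asks for a current negative pregnancy test, and exclusion 16 puts that test within 7 days of the first dose. Hepatitis B has no equivalent.

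**Step 2: apply the rules to four patients.**

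| Before transplant | Now | What the plan does |
|---|---|---|
| HBsAg positive | any | Excluded by exclusion 12 and section VII |
| HBsAg negative, HBcAb positive | any | HBV DNA required; excluded if positive, monitored if negative |
| Both negative | Both negative | Correctly included |
| Both negative | Positive since transplant | Old results satisfy V.3; exclusion 12 is not met on them; HBV DNA is not triggered because HBcAb was negative; no calendar test intervenes |

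Only the last row fails. In the second row the DNA test has no stated pre-dose window, but it reads naturally as a test at study entry, so these patients are largely covered.

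**Step 3: can another entry rule catch the last patient?**

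- *Liver limits.* Exclusion 14 includes "ALT >2.0 times upper normal limit" and a bilirubin limit of 1.5 times the upper normal limit. A patient with normal liver tests passes. Both limits are waived when the abnormality is put down to chronic GVHD, and exclusion 3 says that abnormal liver tests "due to chronic GVHD are specifically not excluded from the study".
- *Present-state exclusions.* Exclusion 3 bars active liver disease (with an exception for chronic GVHD), exclusion 7 bars uncontrolled infection and exclusion 11 bars uncontrolled hepatic disease judged a risk. These would stop a patient with overt hepatitis recognised as such. They would not stop a silent infection, or one attributed to chronic GVHD.
- *Prophylaxis.* Section IV.iv states: "All patients on study must receive antimicrobial prophylaxis per BMT guidelines and standards". This covers viral infection in general but does not name hepatitis B, and section VII leaves hepatitis B antivirals to the investigator.
- *Later testing.* The general follow-up monitoring in section VII and the hepatitis serology attached to the liver stopping criteria both come after dosing has begun.

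**Result.** The patient who passes was negative on both markers before transplant, is positive now, and either has no active liver disease or has it attributed to chronic GVHD. Nothing in the plan requires a hepatitis B test on that patient before the first infusion.

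**The case against.** The best reply is that V.3 is a summary that permits prior results and does not compel sites to rely on them. The same list separately calls for an eligibility evaluation, exclusion 12 remains binding, and section VII has its own hepatitis B scheme. An investigator may always retest. Exclusions 3, 7 and 11, the pre-treatment liver tests, mandatory antimicrobial prophylaxis and the HBV DNA rule together leave few patients exposed, and the documents give no conversion rate from which to show that any would be.

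Much of this stands. It narrows the point and limits its weight, but it does not close the gap. A site that relies on old results is following the protocol, and on those results the exclusion is not met.

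A reader might infer more than the documents support, in three ways:

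- *That the day-14 liver rules would let the second infusion proceed despite a marked ALT rise.* Those are on-treatment rules and do not bear on the age of a screening test. The express permission to continue is confined to ALT above 3 and below 5 times the upper limit, with bilirubin below 2 times the limit, no hepatitis symptoms or rash, and weekly liver tests. A note adds that, in patients with no earlier abnormality, new liver-test abnormalities after dosing prompt evaluation. Silence above 5 times the limit is not permission.
- *That a patient negative on HBsAg, HBcAb and HBsAb falls into a missing category.* Section VII does not list that pattern, but exclusion 12 already settles eligibility: the patient does not meet it.
- *That HBcAb-positive patients are unprotected.* They have a required DNA test and scheduled monitoring.

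**Conclusion.** The point holds in a limited form. The screening rule can defeat the protocol's own exclusion for one kind of patient: negative on both markers before transplant, positive since, and without active liver disease or with it attributed to chronic GVHD.

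The number of such patients cannot be estimated from the documents and is likely to be small. The conclusion rests on reading V.3 as written, with transplant-eligibility results sufficient at any age, and on finding no repeat-test requirement in the exclusion criteria, section VII or the Study Calendar. It does not depend on any assumed infection rate.

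A reader might also suppose that the trial's results are affected. The documents give no basis for that, and no effect on the 6-month response rate or the DLT assessment is claimed. This is a cheap improvement to patient safety, not a flaw that undermines the trial.

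**What to change.** For hepatitis B only, replace the prior-testing allowance in V.3 with a requirement for HBsAg and HBcAb drawn with the existing screening bloods, between prednisone start and first ofatumumab. Add HBV DNA if HBcAb is positive now or was positive before transplant. The second condition is there because the Background states that recipient B cells are depleted by conditioning; my inference is that an antibody seen earlier may no longer be detectable. Require the results to be reviewed before the first infusion, apply the section VII rules to them, and add a hepatitis B entry to the calendar's screening column.

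The calendar footnote already allows screening tests between prednisone and ofatumumab, so prednisone need not wait. The cost is a short amendment, a small laboratory charge per patient, and possibly a brief wait for results within the 14 days allowed from prednisone start to ofatumumab.

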This is a phase I-II trial to examine the safety and efficacy of prednisone and escalating dose of ofatumumab for the primary therapy of chronic GVHD. Prednisone will uniformly be initiated at 1 mg/kg/day, and the phase I component will test an escalating dose of ofatumumab at cohorts of 300mg, 700mg, and 1000mg given on day 0 and 14 of study. In the phase II component, patients will be followed for total of 24 months (including study therapy day 0 and day 14, and then months 1, 3, 6, 12 after therapy, then at 18 and 24 months following therapy), and the primary efficacy endpoint of overall response to therapy will be determined at 6 months following initiation of therapy. Additional secondary endpoints and biologic correlative studies will be performed at the indicated time points.

Inclusion Criteria:

1. HCT recipients \geq 18 years of age
2. HCT recipients newly requiring systemic glucocorticoid therapy (at \geq 1mg/kg/day prednisone or equivalent) for chronic GVHD
 - i. See **appendix B** for definitions of chronic GVHD severity for individual organs and determination of global composite score
 - ii. In the phase I component of the trial, only those with overall moderate or severe global composite score are eligible
 - iii. In the phase II component of the trial, patients of any global composite score are eligible, provided they have need for systemic therapy for chronic GVHD
3. Patients can be enrolled and begin study therapy with ofatumumab within 14 days from initiation of 1 mg/kg/day prednisone for therapy of chronic GVHD.

Exclusion Criteria:

1. Relapse of primary hematologic malignancy that served as indication for HCT.
2. Previous systemic glucocorticoid therapy (at \geq 1mg/kg/day prednisone or equivalent) for chronic GVHD.
 - Prior systemic glucocorticoid therapy for acute GVHD is permitted
 - Prior or ongoing systemic immune suppressive agents (including, but not limited to common examples such as calcineurin inhibitors, sirolimus, mycophenolate mofetil) provided for either prevention or treatment of acute GVHD are permitted and part of routine standard of care
 - Patients with progressive, uncontrolled manifestations of acute or chronic GVHD despite \geq 1mg/kg/day prednisone (or equivalent) therapy have steroid-refractory disease, and are therefore not eligible for this study

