- vi. Plan for patients not able to be evaluated for outcome on phase I component:
 1. If an enrolled patient dies or comes off study following occurrence of DLT as defined above, this data will inform the

determination of DLT, and there will be no need to replace such patients.

2. Rather, if an enrolled patient does not experience DLT during follow up, but decides to withdraw from the study for other non-DLT related reasons prior to the minimum follow up of 46 days, such a patient would be replaced by a newly accrued patient.

2. Efficacy

a. Overall response rate

- i. Overall response rate (ORR) at 6 months following initiation of therapy represents the composite outcome of complete and partial response (CR + PR).
- ii. Complete response is defined as resolution of all reversible manifestations in each organ or site of chronic GVHD involvement
- iii. Partial response is defined as improvement in at least one organ or site without progression in any other organ or site

b. Complete response rate

- i. Complete response (CR) at 6 months following initiation of therapy requires complete resolution of all chronic GVHD manifestations in all affected organs.

c. Cumulative incidence of non-relapse mortality and primary malignancy relapse

- i. The cumulative incidence of non-relapse mortality (defined as death in the absence of primary malignancy relapse after transplant) and relapse (defined by usual definitions in clinical practice including, but not limited to morphologic, immunophenotypic, or molecular methods) will be estimated from time of study therapy initiation. These are treated as competing-risk events.

d. Overall survival

- i. Overall survival will be determined from date of study therapy initiation, with death from any cause as the event of interest, and censoring at last follow up date for those with incomplete observations.

e. Utilization of second-line systemic immune suppressive therapies

- i. The use of second-line systemic immune suppressive agents will be captured at each study visit.
- ii. This specifically refers to systemic therapies only, not topical or local therapies, such as topical eye drops, mouth rinses, topical steroid skin cream, or topical vaginal steroid agents.

- iii. Adjustment in prednisone dose according to disease manifestations is not considered second-line therapy

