Following definition of the maximal tolerated dose (MTD) in the phase I component, this MTD will be taken forward in a phase II trial to characterize the efficacy of this approach. The primary endpoint of interest in the phase II component is overall response rate (ORR) to therapy at 6 months. Overall response is defined as the composite of complete response and partial response. In the assessment of response for this primary endpoint, response will be determined according to clinician assessment. The Simon's two-stage optimum design is used to minimize the expected sample size. With a historical baseline ORR proportion of 60% (*justification for this baseline proportion in background section*), anticipated effect leading to ORR of 80% in this investigational treatment (prednisone + ofatumumab), power of 90%, and alpha of 0.1, a total of 38 subjects are needed for this analysis of efficacy. As 6 total patients from the phase I component will have been treated at the recommended phase II dose, these will be included for efficacy analysis. Early termination will occur if 6 or fewer out of 11 ($\leq 6/11$) subjects in first stage have a overall response (CR or PR). If the trial goes on the second stage and a total number of responders (CR or PR) is less than or equal to 26 ($\leq 26/38$), the null hypothesis fails to be rejected. To provide total of 38 subjects for this efficacy analysis, 32 additional patients will be enrolled in the phase II component. Thus, the net total number of patients to be enrolled on the combined phase I-II study will be a maximum of 50.

Statistical Analysis plan:

The 'All Treated population' will be used for the analysis of the efficacy and safety endpoints. Specifically, this will consist of all patients who receive at least one dose of study treatment. For Complete Response (CR) rate and Overall Response rate: A

patient with unknown or missing response will be treated as a non-responder (i.e. the patient will be included in the denominator when calculating the percentage).

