Overall response (ORR) rate will be determined at 6 months and will be reported with associated 95% confidence interval. Complete response rate will be similarly reported. Association between clinical variables (chronic GVHD severity, organ involvement, patient socio-demographic data, disease and transplantation variables) and response will be examined. Patient reported outcomes will be reported, and association between scores on individual measures (chronic GVHD symptom scale, human activity profile, QOL instruments including SF-36 and FACT-BMT) and clinical response to therapy will be explored. Cumulative incidence of relapse and non-relapse mortality will be estimated, accounting for competing risk events. Overall survival from date of therapy initiation will be estimated by Kaplan-Meier method, and survival curves among relevant subgroups will be compared utilizing the log-rank test. In the analysis of survival time between responders and non-responders, landmark analysis will be utilized to avoid biased survival estimation. Other time-to-event secondary endpoints (e.g. failure-free survival) will similarly be estimated using the Kaplan-Meier method. Biologic endpoints (total B cell numbers, B cell subsets, immune globulin levels, BAFF levels) will be summarized. Comparisons between relevant groups will be made at specific time points utilizing parametric (e.g. t-test) or non-parametric (e.g. Wilcoxon rank-sum) as appropriate per the nature of the data. Additionally, change in these values over time will be examined according to response vs. non-response to primary therapy with mixed-model approach.

Early Stopping Rule for Toxicity

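### Relapse ends study participation under V.4, yet overall survival counts every death; without stated follow-up after relapse, OS may be censored at relapse and overestimated

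*Combined protocol and SAP*

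**What the plan says.** - **Termination (V.4).** The criteria for ending a patient's study participation are withdrawal, death, item "c. Relapse of primary hematologic malignancy", and end of study.
- **Treatment (III, Summary of Trial design).** Ofatumumab is "given on day 0 and 14 of study" only, so V.4 cannot mean merely stopping the drug.
- **OS definition (V.2.d).** OS runs from the start of therapy, "with death from any cause as the event of interest, and censoring at last follow up date for those with incomplete observations".
- **OS analysis (VI, Statistical Analysis plan).** "Overall survival from date of therapy initiation will be estimated by Kaplan-Meier method". Subgroups are compared by log-rank test. For response groups: "In the analysis of survival time between responders and non-responders, landmark analysis will be utilized to avoid biased survival estimation". The analysis population is "all patients who receive at least one dose of study treatment".
- **Follow-up.** Section III states: "In the phase II component, patients will be followed for total of 24 months". V.4.d repeats the 24 months but describes them as follow-up on study. The Study Calendar has a Survival row that runs to months 18 and 24. None of these mentions relapse.
- **Safety reporting (VII).** Death is a serious adverse event (SAE). SAEs are collected to the end of follow-up, and for at least 6 months after the last dose, but reporting is no longer required once another therapy begins.

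**The concern.** Kaplan-Meier is unbiased only if censored patients have the same later risk of death as those still followed. A patient who leaves at malignancy relapse usually does not. If termination under V.4 also ends ascertainment of death, last follow-up for that patient is about the relapse date, and any later death is missed. The curve then tends towards survival from pre-relapse deaths alone, which is too high if relapse raises mortality.

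At stake are OS, which is part of secondary objective 2, and its log-rank and landmark comparisons. In the comparisons the direction of bias is unknown, because it depends on how relapse differs between the groups. Relapse incidence, non-relapse mortality (NRM) and failure-free survival already treat relapse as an event or competing event, so missing vital status after relapse does not affect them. The 6-month response analysis is also untouched: a "patient with unknown or missing response will be treated as a non-responder", which is a stated rule and is not questioned here.

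**Working it through.** **Plan's own figures.** The plan gives no OS figure. Its only efficacy design figure is the Simon two-stage design for response. An exact binomial search with response rates 60% and 80%, alpha 0.10 and power 90% returns the stated design: stop at 6 or fewer of 11, and 26 or fewer of 38 does not reject. Attained alpha is 0.0970 and power 0.9042. OS does not enter it.

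**Does any text keep relapsed patients in follow-up?**
- V.4.d and the calendar footnote state which reduced data are collected for phase I patients outside the maximum tolerated dose (MTD) cohort. Nothing equivalent is written for relapsed patients.
- The SAE route would capture some deaths, but the end of follow-up is undefined for someone terminated at relapse.

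The passages are therefore unreconciled. Censoring at relapse is not written, but it follows if V.4 is applied literally.

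**Size, as an illustration.** The 24-month relapse incidence (*rel*), NRM incidence (*nrm*) and share of relapsed patients dead by month 24 (*d*) are assumptions. Cause-specific hazards are constant.

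- Total hazard L = −ln(1 − rel − nrm)/24 per month. The NRM part is n = L × nrm/(rel + nrm), and the relapse part is r = L − n.
- True OS(24) = 1 − nrm − rel × d.
- All relapsed patients lost at relapse: Kaplan-Meier tends to exp(−24n) = (1 − rel − nrm)^(nrm/(rel + nrm)).
- Share q lost: Kaplan-Meier = exp(−∫₀²⁴ [nS₀ + (1−q)mR]/[S₀ + (1−q)R] dt), with S₀ = exp(−Lt) and R = r(exp(−mt) − exp(−Lt))/(L − m). The post-relapse death hazard m is solved to give *d*.

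| rel / nrm / d | True OS | Kaplan-Meier, all lost | Bias, all lost | Bias, half lost | m/n |
|---|---|---|---|---|---|
| 5% / 10% / 50% | 1 − 0.10 − 0.025 = 87.5% | 0.85^(2/3) = 89.7% | +2.2 | +1.1 | 14.2 |
| 10% / 10% / 50% | 1 − 0.10 − 0.05 = 85.0% | 0.80^(1/2) = 89.4% | +4.4 | +2.1 | 13.6 |
| 20% / 10% / 60% | 1 − 0.10 − 0.12 = 78.0% | 0.70^(1/3) = 88.8% | +10.8 | +5.0 | 17.3 |
| 20% / 15% / 70% | 1 − 0.15 − 0.14 = 71.0% | 0.65^(3/7) = 83.1% | +12.1 | +5.6 | 15.5 |

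**Milder cases, same four relapse/NRM pairs.**
- Hazard ratio m/n = 5 (23% to 37% of relapsed dead): +0.9, +1.9, +4.0, +5.5 points with all lost; +0.4, +0.9, +1.8, +2.5 with half lost.
- Ratio 3 (15% to 25% dead): +0.5, +1.0, +2.2, +3.1 with all lost; +0.2, +0.5, +1.0, +1.4 with half lost.
- Ratio 1, or no patient lost: 0.

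**With the SAE route.** Suppose every death to month 6.5 is captured (6 months after the day 14 dose, no new therapy before then) and all relapsed patients are lost afterwards. Then Kaplan-Meier = OS(6.5) × exp(−17.5n), and the four biases in the table become +2.01, +3.99, +9.55 and +10.58 points.

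**A second set of assumptions.** With NRM 15%, relapse 5% to 20% and median survival after relapse 4 to 12 months, the overestimate is +2.0 to +14.0 points.

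**Scale at n = 38.** Unseen deaths with all lost are 38 × rel × d = 1.0, 1.9, 4.6 and 5.3. The 95% half-width, 1.96 × √(OS(1 − OS)/38), is 10.5, 11.4, 13.2 and 14.4 points for the four rows.

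**The case against.** The strongest reply is that no passage prescribes the error. V.2.d censors at last follow-up, not at relapse or at the off-study date, so bias needs the further step that leaving the study ends ascertainment of death. Section III promises 24 months without a relapse exception, and a separate Survival row would add little if it covered only patients still attending visits. The 24-month wording in V.4.d belongs to the same list as the relapse criterion, so this is an ambiguity and not a flat contradiction. The sentence ending SAE reports at a new therapy concerns reporting to the drug supplier, not collection. The size is entirely assumed, and it lies below the sampling half-width in every case in the table.

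Much of this stands. Continued survival follow-up may well be intended, the SAE text may capture more deaths than its reporting exemption suggests, and OS is a descriptive secondary endpoint. What does not follow is that the gap is harmless. None of the favourable text says that it applies after termination, although the authors spelled out residual data collection for non-MTD patients. A wide interval does not offset a one-directional error that it does not reflect.

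One further point is fair. The OS population is all treated patients, while 24-month follow-up is written only for those at the phase II dose. The fix below follows the latter group and leaves the longer-term OS follow-up of non-MTD patients as it is.

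**Conclusion.** The concern holds as an unreconciled rule: V.4 applied literally censors relapsed patients at about relapse, and that censoring is informative if relapse raises the risk of death. The overestimate of 24-month OS is 2.2 to 12.1 points in the four main scenarios with all relapsed patients lost, roughly half that with half lost, 0.5 to 5.5 points at hazard ratios of 3 to 5 with all lost, and zero if vital status is tracked or relapse does not alter mortality. All sizes rest on assumed rates and constant hazards. It should be corrected, but it affects only OS and its comparisons. Confidence is medium, because actual follow-up practice cannot be seen from the documents.

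**What to change.** - **V.4:** state that relapse ends the chronic GVHD, patient-reported and biologic assessments, but that vital status and date of death are collected to month 24 for all patients treated at the phase II dose who have not withdrawn consent to follow-up. This also reconciles V.4 with section III and the Study Calendar.
- **V.2.d:** state that OS is not censored at relapse.

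The cost is two sentences, plus a vital-status check at time points already in the calendar's Survival row for about 2 to 8 of 38 patients (5% to 20% assumed relapse: 38 × 0.05 = 1.9; 38 × 0.20 = 7.6). No sample size, decision rule or treatment rule changes.
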